18.0	APPENDICES	30

LIST OF ABBREVIATIONS AND DEFINITION OF TERMS

AE	Adverse Event
AUC	Area Under Curve
BD	Becton, Dickinson and Company
BG	Blood Glucose
BMI	Body Mass Index
cat	Catalog
CFR	Code of Federal Regulations
CI	Confidence Interval
CRF	Case Report/Record Form
DFSP	Defective or Failed Study Product
EDC	Electronic Data Capture
FDA	Food and Drug Administration
FDAAA	FDA Amendments Act of 2007
GCP	Good Clinical Practice
G	Gauge
HIPAA	Health Insurance Portability and Accountability Act
HCP	Healthcare Practitioner
ICH	International Conference on Harmonization
ICMJE	International Committee of Medical Journal Editors
INJ	Injection
IRB/EC	Institutional or Independent Review Board/Ethics Committee
lbf	Injection Peak Forces
mm	Millimeter
NDC	National Drug Code
NI	Non-inferiority
PHI	Protected Health Information
PI	Principal Investigator
PN	Pen Needle
SAE	Serious Adverse Event
SD	Standard Deviation
SOP	Standard Operating Procedure
UADE	Unanticipated Adverse Device Effect
VAS	Visual Analog Scale

1.0 INTRODUCTION

From a market research study (Van Gogh; 2013) – the results showed that User’s perception could not differentiate BD pen needles from other competitors. Therefore, the pen needle market is currently being driven primarily by cost. This study will be used to support the business replacement strategy for BD’s current 4mm pen needle. A design improvement is being implemented by introducing a flatter hub (base) by eliminating the post on the hub. This study is designed to assess the User’s experience and preference and outcomes are intended to be used for marketing claims. This study will have four study groups based on commercially available 32G pen needle groups: 1) BD Nano, 2) NovoFine, 3) NovoFine Plus & NovoTwist and 4) Other 32G (such as UltiMed, MHC, or other private label).

2.0 OBJECTIVES

2.1 Primary Objectives

For all study groups combined, compare user preference for the BD Nucleus pen needle vs. current commercially available pen needles.

2.2 Secondary Objectives

For each individual study group, compare user preference for the BD Nucleus pen needle vs. current commercially available pen needles.

For all study groups combined and each individual study group, compare the user experience with the BD Nucleus pen needle and the commercially available pen needles for component preference.

- a. Outer Cover Handling
- b. Inner Shield Handling
- c. Hub Comfort

For all study groups combined and each individual study group, compare the user experience with the BD Nucleus pen needle and the commercially available pen needles for the following:

- a. Overall Comfort
- b. Anxiety Associated with a Needle Stick Injury
- c. Injection Pain
- d. Bruising
- e. Bending
- f. Ease of Use
- g. Leakage from this injection site

2.3 Exploratory Objectives

For all study groups combined, assess the user acceptance for the following items for the pen needle (non-comparative):

- a. Teardrop Label Removal Force
- b. Outer Cover Removal Force
- c. Inner Shield Removal Force
- d. Ease of Insulin Delivery

In addition, Pen Needle breakage will be monitored (all groups combined).

A sub-group with Asian ethnicity, all study groups combined, will also be evaluated for the objectives listed in the Primary and Secondary Objectives.

3.0 STUDY DESIGN

3.1 Overall Study Design

This is a multi-site, prospective, open-label, randomized, 2-period crossover (15 days per period) study comparing commercially available 32G pen needles to the BD Nucleus pen needle. Nucleus pen needle will be compared to four *groups* of pen needles: 1) BD Nano (32Gx4mm), 2) NovoFine (32Gx6mm), 3) NovoFine Plus (32Gx4mm) & NovoTwist (32Gx5mm) and 4) Other 32G (such as UltiMed, MHC, or other private label). Approximately 25% of the subjects are expected to be Type 1 patients and the remaining 75% are expected to be Type 2 patients.

The study is targeting 260 subjects. A total of 240 evaluable subjects are needed with an additional 20 subjects for subjects lost to follow up or other significant protocol deviations. Each group will consist of approximately 60 subjects. Each subject will be screened to determine eligibility into the study. Subjects entering the study who are currently injecting with one of the above mentioned pen needles will automatically be enrolled in their respective group. For example, if a subject comes in using the BD Nano, they will be enrolled in Group 1. If their current pen needle group has completed enrollment, they will be eligible for wash-in (see below).

To facilitate recruitment, a 14 day wash-in period will be allowed in the following situations:

- As BD holds the vast majority of the Pen needle market share in the US, enrolling subjects using non BD brands will be difficult. Subject's currently using a 32G pen needle of 4, 5 or 6 mm lengths will be allowed to wash-in if their current pen needle group has completed enrollment of 60 evaluable subjects. These subjects will be eligible to wash-in to the next available applicable group, per the Wash-In randomization schedule. The length of their current pen needle will be maintained.
- For subject's currently using a 31G pen needle of 4, 5 or 6 mm lengths provided the subject is willing to switch to an assigned commercially available 32G pen needle for the duration of the study. These subjects will be eligible to wash-in to an available applicable group, per the Wash-In randomization schedule. The length of their current pen needle will be maintained.

Wash-in subjects will be randomized as follows:

- If subject is currently on a 31G x 4mm or 32G x 4mm they will get randomized to either Group 3 (Novo Fine Plus (32Gx4mm)) or Group 4 (UltiCare Micro 32Gx4mm).
- If subject is currently on a 31G x 5mm or 32G x 5mm, they will randomized to either Group 3 (NovoTwist (32Gx5mm)) or Group 4 (MHC Easy Touch 5mm x 32G).
- If subject is currently on a 31G x 6mm or 32G x 6mm, they will randomized to either Group 2 (Novo Fine (32Gx6mm)) or Group 4 (Simple Diagnostics Comfort EZ 6mm x 32G).

Please refer to the Wash-in randomization schedule.

[figure not shown]
Subjects who will remain on their current 32G pen needle will be required to visit the site a total of three times. Wash-in subjects will have an additional visit (Wash-in Visit) for a total of 4 visits. (see Subject Flow Chart Diagram 1).

The study will consist of two 15 day periods (+/- 3 days, no fewer than 13 days and no more than 17 days) in which the subject will use each pen needle (BD Nucleus pen needle or Commercially available 32G pen needle, order randomized) for injection.

Results will be compared to address the Primary, Secondary and Exploratory objectives. A final report will be issued summarizing all outcomes and conclusions.

[figure not shown]
Diagram 1 Subject Flow Chart

3.2 Specification of Study Endpoints

3.2.1 Primary Endpoints

Preference: At the end of the last study period, each subject will be asked to evaluate his or her perception using a 150mm relative VAS scale. The question “Which pen needle did you prefer overall?” will be asked. The far left (-75mm) of the scale will be labelled “Period 1 pen needle was *strongly* preferred overall”. The 0mm center point will be labelled “No Preference”. The far right (+75mm) of the scale will be labelled “Period 2 pen needle was *strongly* preferred overall”.

[figure not shown]
3.2.2 Secondary Endpoints

At the end of the last study period: Each subject will be asked to evaluate his or her perception using a 150mm relative VAS scale for each of the following endpoints: Overall Comfort, Anxiety Associated with a Needle Stick Injury, Injection Pain, and Ease of Use.

After each injection: Additional secondary endpoints information will be collected for Bruising, Needle Bending/Breaking and Leakage in the Subject Diary.

For Needle Breaking, Bending or Injection Site Bleeding or Bruising, each subject will evaluate his/her perception of each by answering with a yes or no response.

For needle leakage, each subject will record leakage using the following scale (0-5):

3.2.3 Exploratory Endpoints

At the end of each study period, each subject will evaluate his or her perception of each of the following by answering with a yes or no response.

Teardrop Label Removal Force: The subject will be asked “Did you find the *teardrop label* easy to remove?” The response options will either be Yes or No.

Outer Cover Removal Force: The subject will be asked “Did you find the outer cover easy to remove?” The response options will either be Yes or No.

Inner Shield Removal Force: The subject will be asked “Did you find t the inner shield easy to remove?” The response options will either be Yes or No.

Ease of Insulin/Non-insulin Delivery: The subject will be asked “Were you able to deliver the insulin/non-insulin easily?” The response options will either be Yes or No.

3.2.4 Safety Endpoints

At 2nd and 3rd visits, presence and severity of any adverse events will be evaluated, recorded, and followed up as required.

For a complete list of survey questions, please refer to “Form: Questionnaire”.

3.3 Acceptance Criteria

Primary Objective: Non-Inferiority Criterion (based on relative VAS where -75mm indicates a strong preference for Period 1 pen needle and +75mm indicates a strong preference for Period 2 pen needle) is -10mm.

Secondary Objectives:

For Overall Comfort, Anxiety Associated with a Needle Stick Injury, Injection Pain, and Ease of Use the Non-Inferiority Criterion is also -10mm.

For Needle Breaking, Needle Bending, Injection Site Bleeding, Bruising and Leakage Score > 1: The difference in occurrence rate with BD Nucleus pen needle vs Occurrence rate with Current pen needle will be compared to a 4% non-inferiority (NI) criteria.

Exploratory Objectives: No formal acceptance criteria has been established for this study.

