13.3 Statistical Methods

All analyses will be performed and presented per subgroup (Group 1 – Group 4) first (with no alpha adjustment). For each response, a statistical test will be applied to determine whether it is valid to combine the results from the four study group into one overall result. If significant differences between the groups are identified, combined results will only include results from the groups exhibiting no significant difference; groups that are significantly different (if any) will not be grouped into the overall result.

If a sufficient number of subjects having a two-weeks wash-in period, are enrolled in the study, a comparison of the responses may be performed. The comparison will be conducted between the subjects who did wash-in and those who did not wash-in for all groups pooled together.

Descriptive statistics (number of observations, mean, standard deviation, minimum, maximum and 95% mean confidence interval) will be calculated and presented for all quantitative responses. Frequency tables with number of observations, percentage of total and 95% confidence interval (score method) for the percentage (as applicable) will be created for discrete responses.

Analysis for relative VAS: For each outcome measured on a relative VAS, a two-sided 95% confidence intervals will be calculated for the average rating. A modeling approach may be used to adjust for the visit effect (because of the often observed bias towards favoring the last PN used). Results will be tested for non-inferiority, followed by superiority:

If the lower bound of the CI is $> -10\text{mm}$, we can conclude in non-inferiority

If the lower bound of the CI is $> 0\text{mm}$, we can conclude in superiority

Analysis for needle breaking, needle bending, injection site bleeding, and bruising: A 95% confidence interval for the following difference in two independent proportions will be calculated using the score method:

$$\text{Proportion with BD Nucleus PN} - \text{Proportion with Current PN}$$

The upper bound of the confidence interval will be compared to the 4% NI criterion: non-inferiority will be concluded given the upper bound of the 95% score interval for the difference in proportions is $< 4\%$.

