3.5 Acceptance Criteria

3.5.1 Primary Objective

Non-Inferiority Criterion (based on relative VAS where -75mm is strongly preferred Current/Assigned and +75mm is strongly preferred Nucleus) is -10mm and the Superiority Criterion is 0mm.

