6.2 Analysis Population Set(s)

Two population will be defined:

- Per-Protocol (PP) Population: Excludes subjects or outcomes based on significant protocol deviations
- Intent-to-Treat (ITT) Population: Includes all randomized subjects, regardless of protocol deviations or whether they followed the randomization.

The primary analyses will be performed on the PP population and all conclusions drawn from those analyses. Analysis based on IIT population will be for information only and presented in Appendix. The number of subjects enrolled, randomized, withdrawn, who completed and who are excluded will be summarized per PP and ITT populations.

Demographic information and Diabetes history collected for all subjects randomized will be tabulated.

Data from all subjects will be included in the summary of safety parameters.

Analysis of relative VAS will only include subjects who completed both study periods.

VAS score, $Y_{analysis}^*$ (mm), will be calculated as:

$$Y_{analysis}^* = \frac{150}{20} * Y_{recorded} - 75 \quad (1)$$

The sign of the VAS responses $Y_{analysis}^*$ will then be adjusted depending on which pen needle was used in the first and in the second period, so that the positive scores (+) will reflect preference for BD Nucleus and the negative scores (-) will reflect preference for the current pen needle. Let $Y_{analysis}$ be the final relative VAS score used for the analysis. Then:

$$Y_{analysis} = \begin{cases} Y_{analysis}^*, & \text{if BD Nucleus is provided in the 2}^{nd} \text{ period} \\ -Y_{analysis}^*, & \text{if BD Nucleus is provided in the 1}^{st} \text{ period} \end{cases} \quad (2)$$

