7.2.2.1 Analysis of Relative VAS Score

For each outcome measured on a relative VAS, a two-sided 95% confidence intervals will be calculated for the average rating. A modeling approach will be used to adjust for the order effect (because of the often observed bias towards favoring the last PN used). A linear model will be used to evaluate the pen needle group effect on the response to test whether the groups can be combined (a p-value < 0.05 for the pen needle group effect indicates non-poolability). In the model, the order of the pen needles used and the group to which the subject belongs based on their currently used or assigned pen needle will be used as covariates. LS means with CI will be obtained from the model and tested for non-inferiority, followed by superiority.

- If the lower bound of the CI is $> -10\text{mm}$, we can conclude in non-inferiority.
- If the lower bound of the CI is $> 0\text{mm}$, we can conclude in superiority.

Additional analysis: a *wash-in* indicator and an *Asian* indicator may be used to investigate these effects, as well as a site effect.

```
> #####
> ## Example R code to fit a linear model
> #####
> ##
> ## fitting the model
> model.fit=lm(vas_analysis ~ (NUCL_ORDER + PN_GROUP + ASIA)^2 + WASH_IN,
+             data=dataset, na.action=na.omit)
> #ANOVA table
> ## if p-value for PN_GROUP < 0.05, results not poolable across Groups
> anova(model.fit)
```

Analysis of Variance Table

Response: vas_analysis

	Df	Sum Sq	Mean Sq	F value	Pr(>F)
NUCL_ORDER	1	192	191.7	0.0928	0.7612
PN_GROUP	3	2757	919.0	0.4446	0.7215
ASIA	1	3215	3215.0	1.5554	0.2144
WASH_IN	1	751	750.8	0.3632	0.5477
NUCL_ORDER:PN_GROUP	3	3991	1330.3	0.6436	0.5882
NUCL_ORDER:ASIA	1	131	130.8	0.0633	0.8017
PN_GROUP:ASIA	3	308	102.6	0.0496	0.9853
Residuals	139	287317	2067.0		

```
> ##example contrast for the different pen needle groups
> ## given results not poolable,
> ## to identify which groups are not poolable
> ##
> model.fit=lm(vas_analysis ~ NUCL_ORDER + PN_GROUP,
+             data=dataset,
+             na.action=na.omit)
> ##
> library(multcomp)
> confint(glht(model.fit, linfct = mcp(PN_GROUP = "Tukey")))
```

Simultaneous Confidence Intervals

Multiple Comparisons of Means: Tukey Contrasts

```
Fit: lm(formula = vas_analysis ~ NUCL_ORDER + PN_GROUP, data = dataset,
na.action = na.omit)
```

Quantile = 2.5914

95% family-wise confidence level

Linear Hypotheses:

	Estimate	lwr	upr
Group 2 - Group 1 == 0	-9.0440	-33.6940	15.6060

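### Protocol 3.3 and SAP 3.5.1 put the primary -10 mm non-inferiority criterion on different scales; the SAP's is the right one, and the protocol should be brought into line

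*Protocol*

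**What the plan says.** **Protocol.** Section 3.2.1 describes the questionnaire: a 150 mm line with the Period 1 needle at the left end and the Period 2 needle at the right. Section 3.3 carries that axis into the acceptance criterion. It is "based on relative VAS where -75mm indicates a strong preference for Period 1 pen needle", and the sentence ends "75mm indicates a strong preference for Period 2 pen needle) is -10mm". The four VAS secondary endpoints named in 3.3 (comfort, needle-stick anxiety, pain, ease of use) take the same -10 mm. Section 13.3 gives the analysis: "For each outcome measured on a relative VAS, a two-sided 95% confidence intervals will be calculated for the average rating". Non-inferiority follows if the lower bound exceeds -10 mm, and superiority if it exceeds 0 mm. An adjustment for the visit effect is optional there. The protocol has no step that reverses the sign for subjects who used Nucleus first.

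**SAP.** Section 3.5.1 states the same -10 mm, but "based on relative VAS where -75mm is strongly preferred Current/Assigned and +75mm is strongly preferred Nucleus". Equation (2), under SAP 6.2, negates the score when Nucleus was used in Period 1, so that "positive scores (+) will reflect preference for BD Nucleus". Section 7.2.2.1 fits a linear model with needle order and group to that re-signed score: "LS means with CI will be obtained from the model and tested for non-inferiority, followed by superiority". SAP 3.5.2 applies the criterion to seven VAS secondary endpoints.

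**The concern.** The two documents state the primary pass/fail rule on different axes, and only one of them measures preference for Nucleus. Needle order is randomized. On the period axis the Nucleus effect therefore enters with opposite signs in the two sequences and, with balanced order, drops out of the mean. What remains is any tendency to favour one period over the other. The protocol expects such a tendency and explains its optional adjustment as needed "because of the often observed bias towards favoring the last PN used".

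The results are meant for marketing claims (Protocol 1.0), the study is open-label, and Protocol 15.7 says the first multi-center publication is to be analyzed as the protocol stipulates. Someone who takes the acceptance criterion from the protocol alone would find a rule that does not address the primary objective. The same applies to the VAS secondary endpoints.

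**Working it through.** **Inputs.** From Protocol 13.1 and SAP section 4: SD 35 mm; true mean 5 mm in favour of Nucleus; margin 10 mm; two-sided 95% CI; n=60 for 90% power and n=45 for 80%. From Protocol 3.1: 240 evaluable subjects. Assumed, because the documents give no value: 1:1 order, a Nucleus effect of d = -20 mm, and a period effect p of 0 or 5 mm toward the second needle.

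**1. The plan's own power.** Power = Φ((5 + 10)/(35/√n) − 1.96).

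- n=60: 35/√60 = 4.518; 15/4.518 − 1.96 = 1.36; power 91.3% (90.4% by noncentral t).
- n=45: 35/√45 = 5.217; 15/5.217 − 1.96 = 0.915; power 82.0% (80.3% by noncentral t).

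The stated 90% and 80% are reproduced. The calculation takes the mean as preference for Nucleus, so the sample size already rests on the SAP's orientation.

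**2. What the raw-scale mean estimates.** The mean rating is p + d when Nucleus is used second and p − d when it is used first. With 1:1 order the average is ((p + d) + (p − d))/2 = p, and d is gone. Adjusting for order on the raw scale does not bring it back, because the equally weighted mean of the two sequences is still p.

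**3. Pass probability of the literal protocol rule.** With order fixed at 1:1, the mean varies with SD 35/√n. The computed interval uses the overall SD, which includes the gap between sequences: about √(35² + d²) = √(1225 + 400) = 40.31 mm. Hence approximately

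P(pass) = Φ((p + 10 − t × 40.31/√n)/(35/√n)).

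- n=240, p=0: half-width 1.970 × 2.602 = 5.126; (10 − 5.126)/2.259 = 2.157; P = 0.985.
- n=60, p=0: half-width 2.001 × 5.204 = 10.414; (10 − 10.414)/4.518 = −0.092; P = 0.46.
- n=60, p=5: (15 − 10.414)/4.518 = 1.015; P = 0.845.

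Simulation with 20,000 trials per case gives 0.985, 0.462 and 0.842. At n=240 with p=5 it gives 1.000.

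**4. Pass probability of the SAP rule.** The re-signed, order-adjusted mean estimates d for any p, and P(pass) ≈ Φ((d + 10)/(35/√n) − t). At d = −20 and n=60 this is Φ(−10/4.518 − 2.00) = Φ(−4.21), about 0.00001; at n=240 it is smaller still. Simulation gives 0.000 in every case. With d exactly at −10 mm the simulated rate is about 2.5%, as it should be.

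**5. The literal rule fails in the other direction too.** With Nucleus truly 5 mm better, n=240 and p=0, simulated superiority is concluded 2.4% of the time on the period axis and 59% of the time on the SAP axis.

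**The case against.** The strongest reply is that no planned analysis uses the period-axis mean. Protocol 13.0 leaves detailed methods to the SAP, and the SAP re-signs the score, states the criterion on the re-signed scale and tests order-adjusted means of it. The protocol's own text points the same way. The objective in 2.1 is preference for Nucleus against commercial needles, and 13.1 assumes a mean in favour of Nucleus. The visit-effect adjustment in 13.3 makes sense only for a Nucleus-signed score, since on the raw axis with balanced order the mean is the visit effect. The likeliest explanation is that 3.3 repeated the questionnaire labels from 3.2.1.

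All of that stands, and it rules out stronger readings. A reader might infer that the trial would pass a needle that users dislike. The documents do not support this: the SAP rule would pass a needle rated 20 mm worse essentially never. A reader might also infer that the literal rule tests whether the second needle is favoured. It does not; a lower bound above -10 mm shows only that this needle is not disfavoured by more than 10 mm. Nor does the literal rule always pass: with 60 subjects, no period effect and Nucleus 20 mm worse, it fails slightly more often than it passes.

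What the reply does not remove is the contradiction. Leaving methods to the SAP does not reconcile two acceptance criteria stated on different axes.

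**Conclusion.** This is a conflict between the protocol and the SAP over the scale of the primary decision rule, and the protocol's statement is the wrong one. The SAP's criterion is correct, matches the protocol's objective and power statement, and gives a valid result if followed.

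Read alone, the protocol rule carries almost no information on Nucleus. For a needle rated 20 mm worse it would pass about 98% of the time at n=240 with no period effect. At n=60 it would pass about 46% with no period effect and about 84% with a 5 mm last-needle bias. The SAP rule passes about 0% in each case. These figures assume 1:1 order and SD 35 mm. The 20 mm and 5 mm are illustrative; the documents give no size for the last-needle bias. They measure how far apart the two written rules are, not the error rate of the analysis the SAP would run.

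**What to change.** Amend Protocol 3.3 so that -75 mm means the current or assigned needle is strongly preferred and +75 mm means Nucleus is strongly preferred, as in SAP 3.5.1. Add to Protocol 13.3 that each rating is re-signed by needle order, as in SAP equation (2), before any mean or confidence interval is compared with -10 mm or 0 mm. Say that both apply to the primary endpoint and to all VAS secondary endpoints. The Period 1/Period 2 labels in 3.2.1 can stay, because they describe the form that subjects complete.

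The cost is two sentences in a protocol amendment. The SAP's VAS criterion, the margin, the sample size and data collection need no change.
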